#### **4.4.6.3     *Interim Analyses and Final Analysis***

The sponsor will perform an interim analysis after all subjects have completed Part 1. Part 1 subject data will be locked and Part 1 treatment assignments will be unblinded to the study team to allow for statistical analysis of the primary endpoint, specific to the Part 1 interim analysis and treatment groups. The whole result package (all SAP-defined analysis, specific to Part 1) will be delivered. Hypothesis testing will be based on the active arms in Part 1 versus the part 1 placebo group.

The final analysis will be conducted after all subjects have completed Part 1 and Part 2, if applicable. The two study parts will be pooled, and statistical analysis including hypothesis testing will be performed between each active arm versus the pooled placebo groups from Part 1 and Part 2 (if applicable) for the primary endpoint. The whole result package (all SAP-defined analysis incorporating both Part 1 and Part 2 subjects) will be delivered.

#### **4.4.6.4     *Multicenter Studies***

This is a global, multicenter study with approximately 64 sites planned, dependent on the completion of both. Efficacy data collected from all study sites will be pooled for data analysis. The effect of study site on the efficacy analysis results may be explored post-hoc, as needed.

#### **4.4.6.5     *Multiple Comparisons/Multiplicity***

No adjustment for multiplicity will be performed to control overall family-wise type I error due to the hypothesis generating nature of this study. Each pairwise comparison between EP262 and placebo will be conducted at a 10% level.

#### **4.4.6.6     *Use of an “Efficacy Subset” of Subjects***

The primary efficacy analysis will be performed on the Full Analysis Set. No additional efficacy subsets or sensitivity groups will be applied to the primary endpoint.

#### **4.4.6.7     *Active-Control Studies Intended to Show Equivalence***

This study does not include an active-control product and is not intended to demonstrate equivalence between any two drug products.

#### **4.4.6.8     *Examination of Subgroups***

Given the small sample size, no formal subgroup analyses are planned for this study.

#### **4.4.7     *Plasma Concentrations***

Raw plasma concentration values will be summarized for the PK Set by EP262 dose level and sampling time point using descriptive statistics, to include the geometric mean and CV (%). The geometric CV is calculated as  $100 * \sqrt{\exp(\sigma^2) - 1}$ , where  $\sigma^2$  is the variance of the log-transformed data. For summaries of plasma concentrations, values below the BLQ will be set to missing. The number and percentage of subjects with BLQ values will be summarized by time point and EP262 dose level.

#### **4.4.8 Pharmacokinetic Analysis**

Pharmacokinetic analysis will be based on analysis of the EP262 concentration data as outlined in [Section 4.4.7](#).

### **4.5 Safety Evaluation**

Safety analysis will be carried out for the Safety Analysis Set, to include all subjects who receive at least one dose of study drug. Subjects who do not complete the study, for whatever reason, will have all available data up until the time of termination included in the analysis. For safety analysis presented by study visit, the baseline value will be defined as the last value reported prior to first dose of study drug.

#### **4.5.1 Extent of Exposure**

Extent of exposure to study treatment will be summarized for the Safety Analysis Set by treatment group within each study part, pooled treatment groups, and over all subjects combined.

Total dose received (mg) will be determined as the summation of all entries of “Dispensed Amount (Capsules)” reported on the “Drug Accountability – Dispensed” eCRF minus the summation of all entries of “Amount Returned (Capsules)” reported on the “Drug Accountability – Returned” eCRF. Any capsules reported as lost will be further subtracted from this total. Subjects that are missing their return records are assumed to have taken all dispensed capsules for the missing bottle. This value is considered to be the Action Number of Capsules Taken per subject. The Actual Number of Capsules Taken is then multiplied by the following within each group to obtain the total dose received (mg):

- Subjects assigned to the EP262 150 mg treatment group in Part 1 have their total amount of capsules multiplied by 75 mg (i.e., each capsule received contains 75 mg of study drug).
- Subjects assigned to the EP262 50 mg treatment group in Part 1 or the 25 mg treatment group in Part 2 have their total amount of capsules taken multiplied by 25 mg (i.e., each capsule received contains 25 mg of study drug).

Duration of exposure and total dose received (mg) will be summarized using descriptive statistics. The duration of exposure will be presented in days and calculated as the date of last dose of study drug minus the date of first dose of study drug, plus one. Duration of exposure and total dose received (mg) will be summarized using descriptive statistics.

#### **4.5.2 Measurements of Treatment Compliance**

Compliance to the study treatment regimen will be based on the drug accountability records. Compliance will be determined as the percentage of expected capsules that a subject should have taken based on their dosing days on study relative to the drug accountability reporting of their actual number of capsules taken. The following definitions are applied:

- Expected Number of Dosing Days: the last dose date reported on the End of Treatment eCRF minus the onsite first study administration that takes place at Visit 2 (Day 1) + 1.
- Expected Number of Capsules to be Taken: Expected Number of Dosing Days multiplied by:
  - Part 1: two (standard dosing includes two capsules per day)
  - Part 2: one (standard dosing includes one capsule per day)
- Actual Number of Capsules Taken: The summation of all entries of “Dispensed Amount (Capsules)” reported on the “Drug Accountability – Dispensed” eCRF minus the summation of all entries of “Amount Returned (Capsules)” reported on the “Drug Accountability – Returned” eCRF. Any capsules reported as lost will be further subtracted from this total. Subjects that are missing their return records are assumed to have taken all dispensed capsules for the missing bottle.

Treatment compliance (%) is defined as the Actual Number of Capsules Taken divided by the Expected Number of Capsules to be Taken, multiplied by 100.

Dosing compliance will be summarized using descriptive statistics, by treatment group within each study part, pooled treatment groups, and over all subjects combined for the Safety Analysis Set. The number and percentage of subjects who are < 80% compliant,  $\geq 80\%$  compliant to < 120% compliant and  $\geq 120\%$  compliant within each treatment group and overall subjects combined will be summarized.

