The Double-Blind Treatment Period will consist of 3 study visits (Visits 2, 3, and 4 [Day 1, Week 3, and Week 6]). During this period, all subjects who meet eligibility requirements will be enrolled into the study and will be randomized on Visit 2 (Day 1) to receive double-blind, QD, PO doses of EP262

or placebo for 6 weeks. In Part 1, subjects will be randomized in a 1:1:1 ratio to receive a 150 mg dose of EP262, 50 mg dose of EP262, or placebo PO, QD. In Part 2, subjects will be randomized in a 3:1 ratio to receive either a 25 mg dose of EP262 or placebo PO, QD. Randomization will be conducted centrally via an Interactive Web Response System (IWRS) and stratified based on prior use of omalizumab (yes/no). QD PO dosing of study drug should occur after at least a 4 hour fast and administered at approximately the same time of day. Subjects should refrain from eating for at least 2 hours postdose. The time and date of all dose administrations will be recorded in a daily diary. The first dose of study drug will be administered at the clinical site on Visit 2 (Day 1) after all baseline study procedures are completed. Visit 2 (Day 1) will not have a visit window; all other visits in the Double-Blind Treatment Period will have a visit window of ± 3 days. Subjects who discontinue from treatment early should have the Early Treatment Termination Visit conducted as soon as possible after the last dose of study drug, ideally within 2 days after the last dose of study drug. Throughout the treatment period, subjects must remain on their prescreening background therapy, although rescue medication may be taken as needed.

Safety Follow-Up Period

Any subject who completes the Double-Blind Treatment Period or discontinues study drug (EP262 or placebo) early will have a Safety Follow-Up Visit approximately 4 weeks (± 3 days) after the last dose of study drug.

Number of Subjects (Planned):

Approximately 154 subjects with CSU will be randomized into this study. Approximately 114 subjects will be randomized in Part 1 and approximately 40 subjects will be randomized in Part 2. **Enrollment of subjects with prior omalizumab use will be limited to 20 subjects (15 subjects in Part 1 and 5 subjects in Part 2).**

Main Criteria for Inclusion and Exclusion:

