9.2. Treatment Compliance

The Investigator should assess the subject's compliance with dosing of study drug by counting returned study drug capsules and reviewing the subject's dosing diary as indicated in the Schedule of Assessments ([Appendix A](#)).

If the Investigator has concerns about a subject's dosing compliance, the Investigator should discuss this with the subject, assess the reasons for noncompliance and the likelihood that the subject will remain noncompliant, and notify the Sponsor accordingly.

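### An unreturned bottle counts as fully taken while expected capsules stop at the last dose, so early stoppers can show impossible compliance and total dose

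*SAP*

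**What the plan says.** SAP 4.5.2 names its source: "Compliance to the study treatment regimen will be based on the drug accountability records". The count of capsules taken is dispensed minus returned, less any reported lost. For a bottle without a return record, "Subjects that are missing their return records are assumed to have taken all dispensed capsules for the missing bottle". The same sentence stands in SAP 4.5.1, where the count is multiplied by capsule strength to give total dose in mg.

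The expected count is built from dosing days, defined as "the last dose date reported on the End of Treatment eCRF minus the onsite first study administration that takes place at Visit 2 (Day 1)", plus one. These days are multiplied by two capsules in Part 1 and one in Part 2. Compliance is the "Actual Number of Capsules Taken divided by the Expected Number of Capsules to be Taken, multiplied by 100". No upper limit is set. Subjects are then grouped as below 80%, 80% to below 120%, and 120% or more.

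The protocol also has a dosing diary. In the Synopsis and 7.1.2: "The time and date of all dose administrations will be recorded in a daily diary". Protocol 9.2 has the investigator assess compliance "by counting returned study drug capsules and reviewing" that diary. SAP 4.5.1 and 4.5.2 do not use the diary.

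**The concern.** The numerator and denominator follow different clocks. The denominator ends when the subject is known to have stopped. The numerator, for a bottle with no return record, runs to the end of the bottle. The excess is not a cautious guess about unknown intake, because it assigns capsules to days on which the trial's own last dose date says none were taken.

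The outputs at stake are total dose received (mg), percent compliance and the band of 120% or more. Duration of exposure in SAP 4.5.1 is computed from dates and is not affected, so the same subject could show a short duration beside a total dose that could not have been taken on schedule in that time. A reader of the top band could not tell extra dosing from a missing form. The rule also hides missed doses, since every capsule in the unreturned bottle counts as taken.

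**Working it through.** The plan states no compliance or exposure figure to reproduce, so the SAP formula is applied directly.

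**Inputs**
- Capsules per day: 2 in Part 1, 1 in Part 2 (SAP 4.5.2).
- Capsule strength: 75 mg in the 150 mg arm; 25 mg in the 50 mg and 25 mg arms (SAP 4.5.1). Check: 2 × 75 = 150, 2 × 25 = 50, 1 × 25 = 25 mg per day.
- Dispensing: Visit 2 (Day 1) and Visit 3 (Day 22, ±3 days) only (Protocol Appendix A).
- Capsules dispensed: not stated. Assumption: the first supply covers at least 21 days (to reach Day 22); 24 days (late end of the window) and 30 days are shown as a range.

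**Formula.** Take a stop on Day d before Visit 3, a first supply of S days, its whole return record missing, and c capsules per day:

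compliance = 100 × (c × S) / (c × d) = 100 × S / d, the same in both parts.

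| Last dose | S = 21 | S = 24 | S = 30 |
|---|---|---|---|
| Day 7 | 300% | 343% | 429% |
| Day 10 | 210% | 240% | 300% |
| Day 14 | 150% | 171% | 214% |
| Day 18 | 117% | 133% | 167% |
| Day 21 | 100% | 114% | 143% |

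With S = 21, every stop up to Day 17 lands in the top band (21 / 1.2 = 17.5).

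**Total dose, Day 7 stop, S = 21**
- 150 mg arm: credited 42 × 75 = 3,150 mg; expected through the last dose 14 × 75 = 1,050 mg.
- 50 mg arm: 42 × 25 = 1,050 mg against 14 × 25 = 350 mg.
- 25 mg arm: 21 × 25 = 525 mg against 7 × 25 = 175 mg.

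Beside a 7-day duration, 3,150 mg implies 3,150 / 7 = 450 mg per day on a 150 mg regimen.

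**Second supply only missing.** With 21 days' capsules accounted for from the first supply and S = 21, compliance is 100 × 42 / d: Day 22 = 191%, Day 28 = 150%, Day 35 = 120%, Day 42 = 100%.

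**Several bottles per visit.** The rule works bottle by bottle. Suppose the 42 Part 1 capsules came as two bottles of 21, and the Day 7 stopper took all 14 from one. If only the opened bottle's record is missing, compliance is 21 / 14 = 150%. If only the unopened one is missing, it is (14 + 21) / 14 = 250%. Both are below 300%.

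**Effect on an arm mean.** In an arm of 38, one subject at 200% to 300% instead of 100% adds 100/38 = 2.6 to 200/38 = 5.3 points. If all of the roughly 10% expected withdrawals (about 4 of 38) were affected, the shift would be 10.5 to 21.1 points. That is an extreme case, not a forecast.

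**The case against.** The strongest reply is that little depends on these numbers. The primary MMRM is run on the Full Analysis Set under a treatment policy strategy, with no compliance term (SAP 4.4.3). No Per Protocol Set will be formed (SAP 4.7), so compliance excludes nobody. A reader might infer that the rule distorts the efficacy result; the documents do not support that. This stands, and it limits the point to descriptive tables.

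There are also safeguards. Drug is collected at the Early Treatment Termination Visit (Protocol 9.4.4), sites are to pursue unreturned drug (10.5) and document it (10.6), and overdoses have their own reporting route (12.10.2). These should make missing records less common, and overdose detection does not rest on the top compliance band. They do not correct the formula when a record is missing.

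Three stronger readings are tempting and should not be drawn:
- That 200% to 300% is typical of early discontinuers. It depends on an assumed supply, an early stop within a dispensing interval and a missing record. It is neither a forecast nor a bound.
- That those who stop early are the likeliest not to return bottles. This is plausible, but nothing in the documents shows it.
- That the SAP breaches the protocol by leaving out the diary. Protocol 9.2 describes the investigator's assessment at the site. The analysis section, 16.7, says only that a rate will be computed and names no data source.

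Nor do the documents say that diary counts reach the analysis database.

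**Conclusion.** The point holds, within limits. As written, the rule credits capsules for days after the recorded last dose, and nothing in SAP 4.5.1 or 4.5.2 stops it. With the 21-day minimum supply and the whole first-supply record missing, the result runs from 300% (Day 7 stop) down to 100% (Day 21 stop). Total dose is inflated by the same ratio relative to expected dose through the last dose date, and by more relative to true intake if doses were also missed. The size depends on a dispensed amount and bottle configuration that the documents do not give, and on an unknown number of missing records. The harm is confined to descriptive exposure and compliance summaries. It is still worth correcting, because it puts impossible values into two stated outputs and the correction is small.

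**What to change.** Change the one sentence in both SAP 4.5.1 and 4.5.2:
- Where a return record is missing, limit the capsules credited for that bottle so that the subject's total does not exceed expected capsules through the last dose date. Leave counts from documented bottles as they are.
- If dosing-diary counts are confirmed to be in the analysis database, use the diary-recorded count for that bottle instead, under the same cap.
- Report, by arm, the number of subjects who needed the rule.

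Under the cap, the Day 7 stopper shows 14 / 14 = 100% and 1,050 mg in the 150 mg arm, instead of 300% and 3,150 mg.

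The cap needs only fields that the SAP already uses, so the cost is wording, a small programming change and one added count. The downside is that the cap still assumes full adherence up to the last dose. A subject who stopped on Day 10 after taking 5 days' capsules (10 of 20, a true 50%) would move from 210% to 100%, not to 50%. The diary could narrow that gap, but its entries are self-reported and may be absent for subjects who never come back. Reporting the count by arm shows how much of each table rests on the convention.

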#### **4.5.3 Adverse Events**

Treatment-emergent adverse events (TEAEs) are defined as those AEs with onset after the first dose of study drug or existing events that worsened after the first dose during the study. Treatment-emergent AEs will be summarized by treatment group within each study part, pooled treatment groups, and over all subjects combined. Events reported with a partial onset date (e.g., month and year are reported but the day is missing) will be considered to be treatment-emergent if it cannot be confirmed that the event onset was prior to the first dose of study drug based on the available date entries.

Verbatim terms on case report forms will be mapped to preferred terms and system organ classes using MedDRA, version 26.0.

Summaries that are displayed by system organ class and preferred terms will be ordered by descending incidence of system organ class and preferred term within each system organ class. Summaries displayed by preferred term only will be ordered by descending incidence of preferred term. Summaries of the following types will be presented:

- Overall summary of number of unique TEAEs and treatment-emergent serious adverse events (SAEs) and subject incidence of TEAEs meeting various criteria;
- Subject incidence of TEAEs by MedDRA system organ class and preferred term;

- Subject incidence of the most frequently-occurring TEAEs (i.e., TEAEs occurring in  $\geq 10\%$  of the Safety Analysis Set) by MedDRA preferred term;
- Subject incidence of TEAEs by severity grade, MedDRA system organ class, and preferred term;
- Subject incidence of TEAEs by relationship to study drug, MedDRA system organ class, and preferred term;
- Subject incidence of the most frequently-occurring TEAEs related to study drug (i.e., related TEAEs occurring in  $\geq 10\%$  of the Safety Analysis Set) by MedDRA preferred term;
- Subject incidence of severe TEAEs related to study drug by MedDRA system organ class and preferred term; and
- Subject incidence of SAEs by MedDRA system organ class and preferred term.

At each level of summarization (e.g., any AE, system organ class, and preferred term), subjects experiencing more than one TEAE will be counted only once. In the summary of TEAEs by severity grade, subjects will be counted once at the highest severity reported at each level of summarization; in the summary of TEAEs by relationship, subjects will be counted once at the closest relationship to study drug. Related events include those reported as “Related” to study drug; events considered not related are those reported as “Not Related” to study drug.

Adverse event data will be presented in data listings by study part, subject, treatment group, and event. Serious AEs and AEs leading to interruption or discontinuation of the study drug will be presented in separate data listings.

#### **4.5.4 Deaths, Other Serious Adverse Events, and Other Significant Adverse Events**

All deaths during the study, including the post treatment follow-up period, will be listed by subject, to include any corresponding reported details associated with the death. Serious AEs and other significant AEs, including those that led to withdrawal or interruption of the study drug, will be provided in separate subject data listings.

#### **4.5.5 Clinical Laboratory Evaluation**

All descriptive summaries of laboratory results will be based on data analyzed by the central laboratory and presented in conventional units. All data will be included in by-subject data listings. Laboratory measurements identified as abnormal (i.e., outside the normal range) will also be listed separately by subject, laboratory test, and unit. In addition, normal ranges provided by the central laboratory will be presented in a separate listing. In the event any local laboratory testing is required, the corresponding data will be included in applicable analysis.

Clinical laboratory measurements, including serum chemistry, hematology and coagulation, will be summarized by treatment group within each study part, pooled treatment groups, and over all subjects combined. Descriptive statistics will be

presented for observed values and changes from baseline at each visit where parameters were scheduled to be collected per the clinical study protocol.

Where applicable, laboratory results will be classified as “low,” “normal,” or “high” with respect to the parameter-specific reference ranges (i.e., below the lower limit of the normal range, within the normal range, or above the upper limit of the normal range). Three-by-three contingency tables will be presented for each laboratory parameter to summarize the shift from the baseline category to the worst post-baseline measurement, defined as the value numerically farthest outside of the normal range across all post-baseline visits through the end of the study. Summary results will include the count and percentage of subjects within each shift category and treatment group.

The clinical study protocol includes guidance associated with the monitoring and interruption of study drug for suspected DILI. Subjects with the following post-baseline ALT or AST values will be assessed for the following DILI criteria:

- ALT or AST  $>8 \times$  ULN
- ALT or AST  $>5 \times$  ULN for more than 2 weeks
- ALT or AST  $>3 \times$  ULN AND total bilirubin  $>2 \times$  ULN OR INR  $>1.5$
- ALT or AST  $>3 \times$  ULN with the appearance of new onset fatigue, nausea, vomiting, right upper quadrant pain or tenderness, fever, rash, and/or eosinophilia ( $>5\%$ ).

Subjects qualifying in any of the above treatment-emergent DILI criteria will be presented in a data listing.

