6. TRIAL OBJECTIVES AND PURPOSE

Objectives	Endpoints
Primary Objective	
To evaluate the efficacy of EP262 compared to placebo in subjects with chronic spontaneous urticaria (CSU)	
 • Change from baseline to Visit 4 (Week 6) in the sum of the daily UAS over a 7-day period (UAS7)

Secondary Objectives	
To evaluate the safety and tolerability of EP262 compared to placebo in subjects with CSU	
• Type, frequency, and severity of treatment-emergent AEs (TEAEs)• Change from baseline in vital signs, ECGs, and clinical laboratory parameters
To evaluate the efficacy of EP262 compared to placebo in subjects with CSU as assessed by the following: 
• Pruritus severity• Hive severity	
• Change from baseline to Visit 4 (Week 6) in the sum of the daily ISS over a 7-day period (ISS7)• Change from baseline to Visit 4 (Week 6) in the sum of the daily HSS over a 7-day period (HSS7)
Exploratory Objectives	

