APPENDIX A. SCHEDULE OF ASSESSMENTS

Assessment	Screening	Double-Blind Treatment			Safety Follow-Up	Early Tx Term ^a ≤2 days after last dose	Notes
Visit	Visit 1 ^b	Visit 2	Visit 3	Visit 4	Visit 5 ^c		
Study Day	Days -30 to -14	Day 1	Day 22	Day 43	Day 71		
Study Week		Week 0	Week 3	Week 6	Week 10		
Visit Window	None	None	±3 days	±3 days	±3 days		
Screening or General Assessments							
Informed consent	X						
Medical history	X						Includes CSU disease history.
Height	X						Should be measured using a stadiometer with no shoes.
Body weight	X			X	X	X	Should be measured with no shoes and heavy clothing (outdoor clothing such as coats) on and using a calibrated scale.
HIV, HBV, HCV serology	X						
Eligibility check	X	X					
Randomization		X					In Part 1, subjects will be randomized via IWRS in a 1:1:1 ratio to 50 mg EP262, 150 mg EP262, or placebo. In Part 2, subjects will be randomized via IWRS in a 3:1 ratio to 25 mg EP262 or placebo.
Dispense study drug / administer dose at site		X	X				Administer orally QD as intact capsules with approximately 240 mL (8 fluid ounces) of water on an empty stomach.
Collect study drug / assess study drug accountability and compliance			X	X		X	Subjects will record self-administration of study drug daily in a dosing diary that will be reviewed at each clinic visit during the Double-Blind Treatment Period following Visit 2 by clinical site staff.
Provide electronic device/app training	X						

Assessment	Screening	Double-Blind Treatment			Safety Follow-Up	Early Tx Term ^a	Notes
Visit	Visit 1 ^b	Visit 2	Visit 3	Visit 4	Visit 5 ^c		
Study Day	Days -30 to -14	Day 1	Day 22	Day 43	Day 71	≤2 days after last dose	
Study Week		Week 0	Week 3	Week 6	Week 10		
Visit Window	None	None	±3 days	±3 days	±3 days		
Standard 12-lead ECG	X	X		X	X	X	To be performed predose (as applicable) in a supine position after ≥5 min of rest.
Vital signs	X	X	X	X	X	X	Includes sitting systolic and diastolic blood pressure, pulse rate, body temperature, and respiratory rate, measured predose (as applicable) after ≥5 min of rest.
Chemistry, hematology, and urinalysis	X	X	X	X	X	X	Drawn after an overnight fast (≥8 hours) and predose (as applicable).
Coagulation	X	X	X	X	X	X	
Concomitant medications	X	X	X	X	X	X	Record any prior use of omalizumab. Record all medications taken to treat CSU beginning from the date of diagnosis and all other medications taken within 14 days before Screening. Record any use of rescue medications.

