#### **4.1.2 *Summarization by Visit***

Data summarized by study visit will be based on the nominal, scheduled visit label as reported on the eCRF.

Subjects who discontinue from treatment early should have the Early Treatment Termination visit conducted as soon as possible after the last dose of study drug, ideally within 2 days after the last dose of study drug. The Early Treatment Termination visit will be summarized based on the nominal visit label in by-visit summaries.

Whenever possible, subjects should remain in the study and complete the remaining study visits and assessments even when study drug has been discontinued. Subjects who discontinue study drug for any reason and continue with the study visits as planned through Visit 4 (Week 6) (participating only in efficacy and safety, but not PK measures) will participate in the Safety Follow-Up Visit if the last dose of study drug was administered less than 4 weeks before Visit 4 (Week 6) to ensure that at least 4 weeks of follow-up data are collected for all randomized subjects. Subjects who early terminate will be summarized in any nominal visits in which data is reported.

Data collected at unscheduled visits will not be included in by-visit summaries, but will be considered when endpoint derivations potentially include multiple visits (e.g., determination of baseline value, determination of worst post-baseline value, etc.). All data will be included in subject listings.

Analysis of efficacy by-visit assessments that include assignment of analysis visit labels (██████████) will apply the visit windowing described in [Section 3.4.1.1](#) and [Section 3.4.1.3](#), respectively.

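### The laboratory shift tables keep one worst value per subject across both directions, so a marked low can be displaced by a modest high and the by-arm counts of shifts can be too small

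*SAP*

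**What the plan says.** SAP section 4.5.5 sorts each result into one of three classes: "laboratory results will be classified as “low,” “normal,” or “high” with respect to the parameter-specific reference ranges". It then plans one table per parameter: "Three-by-three contingency tables will be presented for each laboratory parameter to summarize the shift from the baseline category to the worst post-baseline measurement". The worst measurement is "defined as the value numerically farthest outside of the normal range across all post-baseline visits through the end of the study". The unit counted is the subject: "Summary results will include the count and percentage of subjects within each shift category and treatment group".

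Under SAP section 4.1.2, results from unscheduled visits stay out of by-visit summaries but can supply the worst post-baseline value.

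The SAP sets no direction of concern by parameter, no scaling to the lower or upper limit of normal (LLN, ULN), no separate low and high tables, and no rule for ties.

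The same section also plans by-visit descriptive statistics, a listing for specific liver criteria, and a listing of out-of-range results: "Laboratory measurements identified as abnormal (i.e., outside the normal range) will also be listed separately by subject, laboratory test, and unit".

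**The concern.** A worst value needs a single ordering from good to bad. The investigator's ECG classification in SAP section 4.5.6.2 has one: normal, abnormal but not clinically significant, abnormal and clinically significant. Low/normal/high has two tails, and the SAP ranks them against each other by raw distance in the parameter's own units.

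That ranking is uneven for analytes that cannot go below zero. A low is at most LLN away from the range, while a high can be any distance away. If one subject has both, one excursion leaves the table, and the direction of clinical interest plays no part in which one.

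At stake is the by-arm count of subjects shifting to low or to high. No other visible planned table counts subjects by low, normal and high. The window also runs to the end of the study, so a value at the Week 10 follow-up visit, about four weeks after the last dose, can replace one seen during treatment.

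**Working it through.** The plan states no figure for this rule, so there is nothing to reproduce. The check applies the rule as written.

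**Inputs from the documents**
- The rule: SAP section 4.5.5.
- Scheduled post-baseline samples for "Chemistry, hematology, and urinalysis": Visits 3, 4 and 5 (Days 22, 43 and 71), plus the Early Treatment Termination Visit where it applies (Protocol Appendix A).
- Planned group sizes: about 30 (25 mg), 38 (50 mg), 38 (150 mg) and 48 (pooled placebo) (SAP section 4.6).

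**Assumed inputs.** The documents give no numeric reference ranges. All ranges and results below are illustrations in conventional units.

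**Formula.** For a low x the distance is LLN - x. For a high y it is y - ULN. The low is lost when y - ULN > LLN - x, that is, when y > ULN + (LLN - x). Since x cannot be below 0, any y above ULN + LLN outranks even a result of zero.

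| Parameter (assumed range) | Low | LLN - low | Low is lost to any high above | As multiple of ULN | High that outranks zero |
|---|---|---|---|---|---|
| Neutrophils (1.8-7.7) | 0.6 | 1.2 | 7.7 + 1.2 = 8.9 | 1.16 | 7.7 + 1.8 = 9.5 |
| Platelets (150-400) | 70 | 80 | 400 + 80 = 480 | 1.20 | 400 + 150 = 550 |
| Potassium (3.5-5.0) | 2.8 | 0.7 | 5.0 + 0.7 = 5.7 | 1.14 | 5.0 + 3.5 = 8.5 |

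**Either side of the tipping point**
- Neutrophils 0.6 and 9.0: distances 1.2 and 1.3, classed high, low lost.
- Neutrophils 0.6 and 8.8: distances 1.2 and 1.1, classed low, high lost.
- Platelets 70 and 490: distances 80 and 90, classed high, low lost.
- Platelets 70 and 470: distances 80 and 70, classed low, high lost.

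**Sensitivity to the assumed range.** For a neutrophil count of 0.5, with LLN from 1.5 to 2.0 and ULN from 7.0 to 8.0, the threshold runs from 9.0/8.0 = 1.125 to 8.5/7.0 = 1.21 times ULN. The conclusion does not depend on one choice of range.

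**Weight of one case.** One displaced subject is 1/48 = 2.1% of pooled placebo, 1/38 = 2.6% of the 50 mg or 150 mg group, and 1/30 = 3.3% of the 25 mg group. These figures are conditional on such a case occurring. They do not estimate how often it will.

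**Same subject with two shifts.** With neutrophils 0.6 and 9.0, the minimum is below 1.8 and the maximum is above 7.7, so the subject is counted once as a shift to low and once as a shift to high.

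**The case against.** The strongest reply is that little is lost from the report as a whole.

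- SAP section 4.1.1 requires minimum and maximum for continuous variables, and section 4.5.5 gives by-visit statistics by arm. A neutrophil count of 0.6 at Week 3 would pull that arm's Week 3 minimum to 0.6 or below.
- Protocol section 12.1.4.1 makes a laboratory value an adverse event if it is clinically significant, changes study drug, needs additional testing or comes with new symptoms. SAP section 4.5.3 counts treatment-emergent events by arm, so many marked abnormalities would be counted there.
- Every out-of-range value is listed.
- The secondary endpoint, "Change from baseline in vital signs, ECGs, and clinical laboratory parameters", is addressed directly by the change-from-baseline statistics. The shift table is an additional display.
- The protocol reports no adverse laboratory trends in Phase 1 (sections 5.2 and 5.4.2), and the SAP rule is explicit and contradicts nothing in the protocol.

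All of this stands, and it limits the size of the point. It does not repair the shift counts. A minimum does not say how many subjects were low, a listing gives no by-arm count, and the adverse-event route depends on investigator judgement.

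A reader might infer that the rule favours the high whenever a subject has both. It does not: 0.6 with 8.8 in the example is classed low. A reader might also infer that mild ALT elevations are seriously at risk from irrelevant lows. A low ALT can displace only an elevation less than LLN units above ULN. A value above 3 x ULN is more than 2 x ULN beyond the limit, which exceeds LLN, so it cannot be displaced. The ALT argument is marginal.

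**Conclusion.** The point holds as a minor weakness in safety reporting. The single-value rule in SAP section 4.5.5 can remove a low, or a high, from the by-arm shift counts when one subject has both for the same parameter. Because of the floor at zero, the high needed to displace a marked low can be modest: about 1.14 to 1.20 times ULN in the tabulated examples.

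The number of subjects affected is unknown and probably small, since opposite excursions must fall within three scheduled post-baseline samples plus any unscheduled or early-termination ones. The thresholds rest on assumed reference ranges. The existence of the effect rests only on the SAP's wording.

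A reader might conclude that marked lows would go unreported, or that the secondary laboratory endpoint is compromised. The documents do not support either, because the values remain in other planned outputs and the endpoint has its own analysis. The primary analysis is untouched.

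**What to change.** In SAP section 4.5.5, replace the single worst-value shift with two shifts per parameter: baseline category to the lowest post-baseline value, and baseline category to the highest post-baseline value. Keep unscheduled values eligible, as section 4.1.2 already allows. Each excursion is then counted in its own direction, and neither tie rules nor comparison of distances is needed.

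Add a footnote that a subject can appear as low in one block and high in the other, so the two blocks should not be summed.

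The cost is a change of SAP wording and a second column block in a table already planned. Output becomes slightly longer. No new data are needed.
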